This proposal aims to apply a sleep intervention to improve chronic pain in Veterans with TBI. We propose to use morning bright light therapy (MBLT), a readily deployable, cost-effective, non-pharmacologic, and home-based sleep intervention, to improve sleep-wake disturbances and therefore ameliorate chronic pain and improve quality of life in Veterans with TBI. There is substantial scientific precedent for MBLT to be effective in improving sleep quality, as outlined by a recent meta-analysis of 53 MBLT-based studies.³¹ Indeed, the potential of MBLT to improve sleep quality in Veterans with TBI remains unexplored, and yet, highly promising. Outcomes will be assessed pre- and post-intervention, and at a 3-month follow-up time point. *Our central hypothesis is that MBLT will improve sleep quality and ameliorate pain, resulting in improved quality of life in Veterans with TBI.*

Specific Aim 1: Determine the effect of MBLT on *sleep quality* in Veterans with TBI.

- Hypothesis: Self-reported sleep quality, and sleep efficiency using actigraphy, will improve following 4-weeks of MBLT compared to sham in Veterans with TBI.

Specific Aim 2: Determine the effect of MBLT on *pain* in Veterans with TBI.

- Hypothesis: Self-reported pain, and pain testing via pressure algometry, will improve following 4-weeks of MBLT compared to sham in Veterans with TBI.

Specific Aim 3: Determine the effect of MBLT on *quality of life* in Veterans with TBI.

- Hypothesis: Self-reported quality of life will improve following 4-weeks of MBLT compared to sham in Veterans with TBI.

Scientific Rationale and Significance:

Sleep-Wake Disturbances Following TBI. It is nearly universally accepted that one of the principal complicating factors associated with TBI is sleep-wake disturbances. The functional and economic impact of sleep disturbances is staggering¹⁸ and well-known to *directly impair quality of life*,¹¹ preclude independent functioning, reintegration into civilian life, return to duty or success in vocational endeavors.

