Title: *Morning bright light to improve sleep quality in Veterans*

Publications:

Data collection ongoing.

Relevance:

This protocol has recruited 91 participants over 18 months, 60 of which underwent MBLT for 4 weeks. The primary purpose of this protocol was to assess feasibility outcomes, including recruitment rate, retention rate, and adherence to the light therapy. Of the participants with TBI, 88% of subjects remained adherent to light therapy for the full 4 weeks. Overall, 91% of subjects said they liked using the lightbox. We additionally found that MBLT improves self-reported sleep, mood, and quality of life in our pilot cohort, however, this study lacks a placebo device for comparison.

Research Design and Methods:

Veterans within the VA Portland Healthcare System (VAPORHCS) and non-Veterans will be recruited for participation in this study. This study will consist of at least 4 visits over the span of ~5-6 mo.

Study Overview and Timeline.

	Visit 1	Visit 2	At Home	Visit 3	Visit 4 Follow up
Time point:	Day 0	Week 2	Week 2-6	Week 6	Week 10
Informed consent	X				
Subject given actiwatch		X		X	
Conduct pain assessment		X		X	X
Subject given lightbox or sham		X			
Questionnaires		X		X	X
Daily use of intervention for 1 hour			X		
Total time	~120 min	~120 min	28 hours	~120 min	~120 min

- *Informed consent and HIPAA authorization.* Written and verbal informed consent will be obtained before all other Visit 1 activities and may take place on an earlier date if DocuSign is able to be used to facilitate the consent conversation.
 - In cases where DocuSign is not feasible, consent conversations will take place in office space available at the VAPORHCS Sleep Disorders Clinic (building 100-6C), in related outpatient clinical space, or in Research Service space approved for human subjects use

(building 101, rooms 432A, 430, 404), or in subjects' homes. Alternatively, consent may take place remotely via phone or video conferencing via mailed documents.

- Where DocuSign is feasible, study staff will initiate email of a DocuSign envelope providing subjects access to the consent and authorization forms ahead of the consent discussion. Subjects will then be guided through downloading the fully executed consent form.

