- Participants will be asked to fill out demographics information which will include their name (including name at birth), date of birth, city/town of birth, email and physical address, phone number, health history, and military history.
- Individuals without a medical record at the VA will be asked permission for study staff to request their medical record pertaining to sleep and traumatic brain injury.

Visit 2

- Visit 2 will occur ~2 weeks after visit 1. It can take place within the VAPORHCS Sleep Disorders Clinic (building 100-6C), in Research Service (building 101, rooms 432A, 430, 404, and 533), remotely via phone/video conferencing, or at the subject's home.
- *Questionnaires.* Subjects will complete baseline questionnaires. They take ~30 min to complete and include past medical history and self-reported measures on sleep, social habits, quality of life, mental health, pain, and other metrics related to subject's prior trauma exposure history. All questionnaires are validated and will be completed via pen and paper. Medical history and testing related to sleep will be accessed from the participants' VA medical records by study staff with VA credentials. Subjects may elect to complete these questionnaires at either this or subsequent visits as needed. Questionnaires may be mailed if completed remotely.
- *Equipment.* Subjects will be randomized to receive a lightbox (LightPad mini, Aurora Light Solutions) or sham-control modified negative ion generator. Devices will be modified by completely disconnecting the electrical wiring required for negative ion generation. This will be verified using a voltmeter. A small fan may be installed to emit a low humming noise as an indicator of activity. They will be instructed to use either device for 60 min every morning after waking up starting 2 weeks following this visit and continuing for 4 weeks. Light sensitive devices, called HOBOs, will be attached to the lightboxes which will track when the lightbox is turned on or off, as a secondary measure of light delivery.

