- *Pain testing.* Ischemic Pain Test. Ischemic pain testing may be used at VAPORHCS and at visits that are conducted remotely. This test will consist of a manual blood pressure cuff that is placed on the subject's non-dominant upper arm and inflated to 300 mmHg. Threshold will be determined by the amount of time that the subject perceives the constriction as mildly painful. Tolerance will be determined by the amount of time that the subject allows the constriction to continue. This will be done during a single trial. The upper limit of allowing the hand the constriction is 5 minutes.
- *Department of Defense Head Trauma Events Checklist (DoD HTEC).* Determination of TBI status occur through a semi-structured diagnostic interview following the DoD HTEC guidelines. This interview will take ~15 min to complete.
- *Reimbursement.* Subjects will be compensated with up to \$20

Visit 3

- Visit 3 will occur ~4 weeks after Visit 2 and will take place within the VAPORHCS Sleep Disorders Clinic (building 100-6C), in Research Service (building 101, rooms 432A, 430, 404, and 533), remotely via phone/video conferencing, or at the subject's home.
- *Measures.* The same series of questionnaires and pain testing conducted at Visit 1 will be repeated.
- *Equipment.* Subjects will return all equipment, including the actiwatch, lightbox and/or sham device.
- *Reimbursement.* Subjects will be compensated with up to \$60

Visit 4

- Visit 4 will occur ~4 weeks after Visit 3 and will take place within the VAPORHCS Sleep Disorders Clinic (building 100-6C), in Research Service (building 101, rooms 432A, 430, 404, and 533), remotely via phone/video conferencing, or at the subject's home.
- *Measures.* The same series of questionnaires and pain testing conducted at Visit 1 will be repeated.
- *Reimbursement.* Subjects will be compensated with up to \$20
- *End of study debrief.* Subjects will be debriefed about our experimental design, given the inclusion of a placebo-controlled condition. We will provide subjects with a written description that we will describe to them in person and address any questions they may have.

Mailed forms and equipment. In an effort to reduce subject's time at the Portland VA we may mail consent forms, questionnaires, equipment and pre-addressed, pre-paid return envelopes directly to their homes. Instructions will be provided via phone or video conferencing.

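### Baseline outcome questionnaires may be put off to later visits with no cut-off, and both later scheduled visits fall after device use has begun

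*Protocol*

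**What the plan says.** Specific Aims sets the measurement plan: "Outcomes will be assessed pre- and post-intervention, and at a 3-month follow-up time point". The Visit 2 section (Research Design and Methods) places the baseline questionnaires at that visit. They "include past medical history and self-reported measures on sleep, social habits, quality of life, mental health, pain" and other items, so one packet holds both history items and the self-reported outcomes. The same paragraph then says "Subjects may elect to complete these questionnaires at either this or subsequent visits as needed" and "Questionnaires may be mailed if completed remotely". Neither sentence carries a deadline, and no rule for late baseline forms appears elsewhere in the protocol.

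Four statements fix the timing:

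- The visit count is open-ended: "This study will consist of at least 4 visits over the span of ~5-6 mo".
- The timeline table puts "Daily use of intervention for 1 hour" in the at-home period, Weeks 2 to 6, with Visit 2 at Week 2.
- The Equipment bullet under Visit 2 has use "starting 2 weeks following this visit and continuing for 4 weeks".
- "Visit 3 will occur ~4 weeks after Visit 2", and Visit 4 follows about 4 weeks after that.

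The Visit 3 and Visit 4 sections say that the questionnaires and pain testing of Visit 1 are repeated. The table and the Visit 2 text place those measures at Visit 2, and the table shows none at Visit 1.

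**The concern.** A baseline is useful for a change score or a covariate adjustment only if treatment cannot have influenced it. The deferral sentence leaves the timing to the participant and names no limit, and every later visit on the schedule falls after the device is in use. Followed as written, the sentence can produce a baseline that is really an on-treatment or post-treatment measurement.

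Each of the three aims has a self-reported outcome, and Aim 3 (quality of life) has no other. Pain testing and actigraphy are not covered by the sentence. Medical and trauma history is in the same packet but is hardly affected by late completion. The problem is confined to the sleep, pain, quality-of-life and mental-health scales.

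No other measurement clearly fills the gap. The table has no Visit 1 questionnaires, and the short screening questionnaire before consent serves eligibility and is not named as a baseline.

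**Working it through.** **Calendar check.** The visit intervals reproduce the weeks in the table: Visit 2 = Week 2; Visit 3 = 2 + 4 = Week 6; Visit 4 = 6 + 4 = Week 10. Set against the two start dates in the protocol:

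| Source of device start | Device use | Visit 3 (Week 6) | Visit 4 (Week 10) |
|---|---|---|---|
| Timeline table | Weeks 2 to 6 | 4 weeks after start, at end of use | 8 weeks after start |
| Visit 2, Equipment | Weeks 4 to 8 (2 + 2, then 4 weeks) | 2 weeks after start | 6 weeks after start |

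Under either start, both later scheduled visits follow first use. A baseline deferred to Visit 3 also coincides with the post-intervention form, so that participant has no pre/post contrast.

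**Size if late forms are used as baselines.** Take d = 0.50, the lower end of the 0.5 to 1.0 range in the Power analysis section. Let q be the share of baselines in both arms taken at the outcome visit. The protocol does not give q, so a range is shown.

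- With a true baseline, the expected between-arm difference in change is d. With a baseline taken at the outcome visit, the effect is in both terms and cancels, giving 0. The average is (1 − q) × d + q × 0 = d(1 − q). This needs no assumption about correlation.
- If only a share s of the effect is present when the late form is completed, the result is d(1 − q·s). For example, q = 20% and s = 0.5 give 0.50 × (1 − 0.10) = 0.45.
- For ANCOVA the result depends on correlations, so it was simulated with 50 per arm and SD 1. The central case has baseline-to-outcome correlation 0.5 and same-visit correlation 0.9 (8,000 trials). The range uses 0.3 and 0.7 with 0.8 and 1.0 (4,000 trials each). At q = 0 both methods returned 0.501.

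| q | 5% | 10% | 20% | 30% |
|---|---|---|---|---|
| Change score, 0.50 × (1 − q) | 0.475 | 0.450 | 0.400 | 0.350 |
| Change score, simulated | 0.476 | 0.450 | 0.398 | 0.353 |
| ANCOVA, central case | 0.488 | 0.472 | 0.440 | 0.410 |
| ANCOVA, range | 0.483–0.496 | 0.463–0.491 | not run | 0.383–0.433 |

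**Size if late forms count as missing baselines.** Suppose missingness is unrelated to outcome and those participants are left out. The estimate stays at about 0.50 (simulated 0.498 to 0.503), and the standard error is multiplied by 1/√(1 − q): 1.026, 1.054, 1.118 and 1.195 at q = 5, 10, 20 and 30%.

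**The case against.** The rest of the protocol points to Visit 2 as the baseline. The table marks separate questionnaire administrations at Visits 2, 3 and 4, and the Step-by-Step Guidance names an initial, a post-study and a follow-up set. On that reading a form completed at Visit 3 is the post-study form, and bias arises only if staff label it as a baseline, which no section tells them to do.

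There is also a harmless reading. The minimum visit count leaves room to split Visit 2. The Visit 2 text leaves two weeks between that visit and first use, forms can be mailed, and phone contact up to twice a week gives a way to chase them.

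The harm also depends on the analysis, which may be set out in an SAP that is not at hand. The deferral rate is unknown, the modelled bias is toward zero, and at 5% deferral the ANCOVA effect is small.

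Most of this stands as a limit on likelihood and size. It does not remove the defect. None of these routes sets a deadline, and the two-week window does not exist under the table's start date. An SAP can decide how to treat a late form, but it cannot recover a pre-use value that was never collected. If the late form is filed only as the outcome, the baseline is missing, which is still a departure from the pre-intervention assessment promised in Specific Aims.

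**Conclusion.** The concern holds. The deferral sentence permits baseline outcome questionnaires after device use has started, and the protocol contains no cut-off. This follows from the visit weeks alone and does not depend on which device start date applies.

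The consequence depends on handling that the protocol does not fix. If late forms are used as baselines, change-score and baseline-adjusted estimates are pulled toward zero. If they are treated as missing, precision is lost, without bias provided the missingness is unrelated to outcome. A post-only comparison is unaffected. The figures are illustrative: they assume d = 0.50, equal deferral in both arms and a deferral rate that the documents do not give. The case for changing the text rests on the missing limit and on its reach across the self-report outcome of all three aims. The correction is worth making, but the defect is one permissive sentence in a plan whose intended baseline is otherwise clear.

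**What to change.** Replace the deferral sentence with wording such as: *Baseline self-report outcome questionnaires (sleep, pain, quality of life, mental health) must be completed and dated before first device use, preferably before the device is handed over or shipped; only medical and trauma history items may be completed at a later visit.* State also which group the social-habits items belong to.

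Add: *An outcome questionnaire first completed after device use is recorded as a missing baseline, not as a baseline value.*

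Two related passages need attention so that the rule can be applied:

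- Correct the reference to Visit 1 in the Measures bullets of Visits 3 and 4, since the table and the Visit 2 text place those measures at Visit 2.
- Reconcile the device start in the timeline table with the start in the Visit 2 Equipment bullet, so that first device use is one defined time. Which start applies is for the investigators to settle.

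The cost is text changes and minor scheduling work to get forms back before first use. Some baselines may become missing, with some loss of precision in baseline-adjusted analyses. No extra participants are needed.

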- *Actigraphy.* Subjects will be asked to wear an individually configured actigraphy watch (Phillips Respiration Actiwatch 2) for the entirety of the study. This actiwatch collects data related to subject's sleep-wake cycle, including activity (via a built-in accelerometer) and light exposure (via a built-in luxometer). Watches are user friendly, requiring no user input to operate, and batteries last for ~6 weeks. Subjects will be reminded to keep clothing from covering up the luxometer on the actiwatch as much as possible.
- *Study diary.* Subjects will be asked to fill out a study diary, with daily entries for the entirety of the study. They will record when they went to bed, when they woke up, when they used the lightbox, and days they went to work. At this point subjects will be educated on principles of good sleep hygiene, such that all subjects start at the same baseline with respect to their understanding of good sleep hygiene principles. Study diaries will be coded via subject's ID with no other identifiable information listed.
- *Pain testing.* Pressure-pain threshold and tolerance will be quantified using a pressure algometer (AlgoMed Computerized Pain Pressure Algometer), a validated device used both experimentally and clinically with the pressure stimulus delivered to the thumbnail/thenar region of the non-dominant hand. Threshold will be determined by the amount of pressure that the subject perceives as mildly painful. Tolerance will be determined by the amount of pressure that causes the subject to withdraw their hand. This test takes ~20 min to complete.
- *Pain testing.* Cold Pressor Test. The cold pressor test may be used at VAPORHCS and at visits that are conducted remotely. This test will consist of an ice bath that subject's are instructed to submerge

their non-dominant hand into. Threshold and Tolerance will be measured with a stop watch. Threshold will be determined by the amount of time that the subject perceives the temperature as mildly painful. Tolerance will be determined by the amount of time that causes the subject to withdraw their hand. This will be done during a single trial. The upper limit of allowing the hand in the icebath is 5 minutes.

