Video Conferencing. If the subject is comfortable and equipped, we may conduct visits using video conferencing, such as VA Video Connect or other VA approved methods (skype, facetime, google hangouts, etc.). A link to the video chat will be emailed participants via Azure RMS encrypted email. For VA Video Connect (VVC), this email is entered into the VCC platform and an email is automatically generated.

At home visits. In special circumstances study personnel may travel to the subject's homes in order to conduct the visit more comfortably. Equipment, data, and specimens will travel in between the home and the VA only.

Phone calls. In between visits subjects will be contacted up to 2 times per week as needed. They will be assessed for understanding and compliance and given the opportunity to asked questions. Questions will be asked about their sleep, pain, and quality of life metrics.

Emails. Communication via RMS Azure encrypted email may be established between the subject and study coordinator in order to allow subjects to freely ask any questions they may have.

Study Population:

Number of subjects. The target population will consist of n=100 subjects. In order to meet this enrollment target we anticipate that up to 400 individuals may need to be recruited (consented) and screened.

Eligibility Criteria. Only Veterans and non-Veterans who are physically and mentally able to provide written and verbal informed consent and have a medical record-confirmed or physician confirmed diagnosis of TBI, will be included in this study. Additional criteria are as follows:

- 1) Current self-reported sleep-wake disturbances (defined by clinically abnormal Insomnia Severity Index and/or Functional Outcomes of Sleep scores)
- 2) Moderate to severe pain (defined as a score of ≥ 4 on an 11-point scale⁹⁰) persisting for longer than 6 months
- 3) Do not have a diagnosis for dementia
- 4) Are not currently using a lightbox or negative ion generator
- 5) Are not night-shift workers
- 6) Are English speaking with phone access
- 7) Are 18 years of age or older
- 8) Do not have macular degeneration or bipolar disorder (both are relative contraindications to regular bright light exposure)
- 9) No suicidal ideation
- 10) No cancer diagnosis in the past 6 months
- 11) At least 6-12 months of being surgery free
- 12) No evidence of drug and alcohol dependency (defined by the substance abuse and dependency scale).
- 13) Are currently living within the United States.

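### The Visit 2 text starts device use two weeks after Visit 2 (Weeks 4 to 8), but the timeline table has Weeks 2 to 6 and the device is returned at Visit 3 (Week 6)

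*Protocol*

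**What the plan says.** All of the following is current Protocol text.

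- **Visit 2, timing:** "Visit 2 will occur ~2 weeks after visit 1". With Visit 1 on Day 0, Visit 2 is at Week 2.
- **Visit 2, Equipment:** participants are randomised, receive the lightbox or the disabled ion generator, and are to use it for 60 minutes each morning, "starting 2 weeks following this visit and continuing for 4 weeks".
- **Study Overview and Timeline (table):** the row "Daily use of intervention for 1 hour" is marked in the at-home column, headed Week 2-6, with a total time of 28 hours. Visit 3 is at Week 6 and Visit 4 at Week 10.
- **Visit 3, timing:** "Visit 3 will occur ~4 weeks after Visit 2".
- **Visit 3, Equipment:** "Subjects will return all equipment, including the actiwatch, lightbox and/or sham device". The Step-by-Step Guidance also collects the device at Visit 3.
- **Visits 3 and 4, Measures:** "The same series of questionnaires and pain testing conducted at Visit 1 will be repeated". The table and the Visit 2 text place those baseline measures at Visit 2, not Visit 1.
- **Specific Aims:** all three hypotheses concern the effect after four weeks of light therapy against sham. The section on precedent for the light therapy fixes the course at 60 minutes a day for four weeks.

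**The concern.** The start date of the randomised treatment has two values that cannot both hold. The table fills the whole interval between Visits 2 and 3 with treatment and leaves no room for a two-week delay. The Visit 2 text inserts that delay without moving Visit 3 or the device return.

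What is at stake is the meaning of the Visit 3 assessment. For a participant who starts when the Visit 2 text says, the post-treatment measurement falls halfway through the course. The second half cannot be delivered because the device has gone back. The four-week effect in the hypotheses is then not measured in that participant, and no later analysis can restore sessions that were not given.

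The safeguard against this is partial. On phone calls the Protocol says "In between visits subjects will be contacted up to 2 times per week as needed". The calls cover understanding and compliance, but they are discretionary and the text ties them to neither schedule.

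**Working it through.** This is calendar arithmetic. Significance level, power, effect size and dropout play no part.

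**Inputs**

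| Quantity | Value | Source |
|---|---|---|
| Visit 2 | Week 2 | Visit 2 text; timeline table |
| Visit 3 and device return | Week 2 + 4 = Week 6 | Visit 3 text; table; Step-by-Step Guidance |
| Daily use | one 60-minute session | Visit 2, Equipment; table |
| Delay in the Visit 2 text | 2 weeks | Visit 2, Equipment |
| Course length | 4 weeks | Visit 2, Equipment; Specific Aims |

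**1. The table's own figure.** Use in Weeks 2 to 6: (6 − 2) × 7 = 28 sessions of 1 hour = 28 hours. This reproduces the stated total exactly, so the table is consistent with itself.

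**2. The Visit 2 text.** Start = 2 + 2 = Week 4. End = 4 + 4 = Week 8.
- Sessions before Visit 3: (6 − 4) × 7 = 14 of 28, or 50%.
- Sessions falling after the device is returned: (8 − 6) × 7 = 14.
- Gap between Visits 2 and 3 needed for a full course: 8 − 2 = 6 weeks, against a stated gap of about 4.

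**3. Sensitivity to visit timing.** Visit times are approximate and the Protocol gives no visit window. The ±1 week below is an assumption.

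| Visit 3 at | Sessions done if the Visit 2 text is followed |
|---|---|
| Week 5 | (5 − 4) × 7 = 7 (25%) |
| Week 6 | 14 (50%) |
| Week 7 | (7 − 4) × 7 = 21 (75%) |
| Week 8 | (8 − 4) × 7 = 28 (100%) |

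The full course is reached only if Visit 3 slips by two whole weeks.

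**4. Two explanations for the clause.**
- *Leftover visit numbering.* If the visit meant were Visit 1 (Day 0), use would run from Week 0 + 2 = 2 to Week 2 + 4 = 6, exactly the table. The references to Visit 1 in the Measures bullets of Visits 3 and 4 point the same way.
- *Deliberate lead-in.* The watch is first issued at Visit 2, its battery lasts about 6 weeks, and 2 weeks before treatment plus 4 weeks on treatment is 6 weeks. Outcomes are to be assessed before and after the intervention, and Aim 1 includes actigraphic sleep efficiency. On this reading the delay is right and the timing of Visits 3 and 4 is wrong.

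Both are inferences. The Protocol does not settle which is correct.

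**The case against.** The strongest defence is that harm arises only if staff follow one clause against the rest of the operating schedule. The table, the Visit 3 timing, the device return in two places and the four-week course all agree with one another. Staff collecting a device halfway through a four-week course would probably notice. Participants are instructed through an information sheet and phone scripts, which the appendix lists but which are not shown, and these may carry the correct date. This stands as a limit on severity. It does not remove the contradiction, because nothing in the Protocol says which text governs.

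A reader might go further in several ways that the document does not support:

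- *That participants received half the course.* The document does not show which schedule they were given.
- *That the Visit 2 sentence is the only statement of when to start.* The table also gives a start, at Week 2.
- *That no reading of the approximate visit times could deliver the full course.* The range of 7 to 21 sessions rests on an assumed window. A two-week slip would stretch the stated interval, but no window is given that excludes it.
- *That the trial is biased between arms or loses a calculable amount of power.* Both arms get the same instruction, and the number affected is unknown.
- *That the clause is simply a typing error and the table must be right.* The lead-in reading also has support. The table has its own difficulty: its end at Week 10 does not match the five to six months stated just above it or the three-month follow-up in Specific Aims. Those are separate matters.

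**Conclusion.** The Protocol contradicts itself on when treatment starts. This is an internal inconsistency that should be corrected; it is not a demonstrated threat to the trial's result.

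If the Visit 2 text is followed and visits fall at their nominal times, Visit 3 comes after 14 of 28 sessions and the other 14 cannot take place. Under an assumed window of one week either side, the count is 7 to 21 of 28. If the table is followed, all 28 sessions are done by Visit 3 and nothing is lost. The number of participants affected cannot be derived from the document.

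**What to change.** State which schedule applies, then align the Visit 2 text, the table, the Visit 3 and 4 text and the participant materials (information sheet and phone scripts) in one amendment.

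**Default, matching most of the Protocol.** Amend the Visit 2 Equipment text so that use starts the morning after Visit 2 and runs for four weeks to Visit 3. In the Measures bullets of Visits 3 and 4, change the reference from Visit 1 to Visit 2. The cost is one clause, two visit references and the matching participant materials, with no added visits or participants. The drawback is that a watch first issued at Visit 2 then gives almost no pre-treatment actigraphy. If the team wants that baseline, the watch must be issued earlier. This means further edits to the table and visit text, more watches in circulation and, if issued at Visit 1, about 6 weeks of wear with no margin on the stated battery life.

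**Alternative, if the delay was an intended actigraphy lead-in.** Keep the Visit 2 text, move Visit 3 and the device return to Week 8 (2 + 2 + 4), and move Visit 4 to Week 12 (8 + 4) so that the four-week follow-up gap is kept. The Measures bullets still need the same correction. The cost is two more weeks per participant and a revised table.

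**Participants already treated.** Confirm each actual start date from the study diary and, in the lightbox arm, the HOBO log. The Protocol describes HOBOs only on lightboxes, and the diary item records "when they used the lightbox" without naming the sham, so check that sham participants recorded device use too.

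### The Visit 2 text starts treatment two weeks later than the timeline table, and no visit instruction issues the actigraphy watch early enough to give a pre-treatment baseline on the table's schedule

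*Protocol*

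**What the plan says.** Aim 1 names actigraphic sleep efficiency after 4 weeks of treatment, compared with sham. The Specific Aims section promises assessment before and after the intervention and at a 3-month follow-up.

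The instructions that set the dates are:

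- **Visit 2, Equipment** (Visit 2 is about 2 weeks after Visit 1): morning use for 60 minutes, "starting 2 weeks following this visit and continuing for 4 weeks".
- **Study Overview and Timeline table**: daily use sits in the at-home column for Weeks 2 to 6, with a total of 28 hours. The row "Subject given actiwatch" is marked at Visit 2 and Visit 3, not at Visit 1.
- **Visit 2, Actigraphy**: "Subjects will be asked to wear an individually configured actigraphy watch (Phillips Respiration Actiwatch 2) for the entirety of the study". Battery life is given as about 6 weeks.
- **Visit 3**: "Visit 3 will occur ~4 weeks after Visit 2", and "Subjects will return all equipment, including the actiwatch, lightbox and/or sham device".
- **Step-by-Step Guidance**: only consent and authorisation at Visit 1; device, questionnaires, pain testing and diary at Visit 2; watch, device and diary collected at Visit 3.
- **Visit 3 and Visit 4, Measures**: "The same series of questionnaires and pain testing conducted at Visit 1 will be repeated", although the table and the step-by-step guide place the baseline measures at Visit 2.
- **Follow-up and length**: "Visit 4 will occur ~4 weeks after Visit 3" (Week 10 in the table), against the 3-month follow-up in the aims and, in Research Design and Methods, "This study will consist of at least 4 visits over the span of ~5-6 mo".

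**The concern.** The start of treatment has two dates two weeks apart, while Visit 3 and the return of the device have one. Each start date costs Aim 1 something different. The later start leaves room for two weeks of untreated actigraphy but cuts the course in half before the outcomes are taken. The earlier start completes the course but leaves no usable untreated actigraphy.

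On the later start, every Visit 3 outcome (sleep, pain and quality of life) would be measured mid-course, so the effect after 4 weeks of treatment would not be observed. On the earlier start, sleep efficiency has no pre-treatment value, so change from baseline and baseline adjustment are unavailable for that outcome.

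**Working it through.** **Inputs.** Visit 1 = day 0; Visit 2 = day 14; Visit 3 = day 14 + 28 = day 42; Visit 4 = day 42 + 28 = day 70. Dose is one hour a day for 28 days. The watch is first issued at Visit 2 (day 14).

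**The plan's own figure.** The table's at-home total is (42 − 14) days × 1 hour = 28 hours. It reproduces, so the table agrees with itself and with the Visit 3 date.

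**Formulas.** Sessions before Visit 3 = min(Visit 3, end of treatment) − start of treatment. Untreated nights = start of treatment − day of watch issue.

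| Schedule | Treatment | Sessions before Visit 3 | Untreated nights |
|---|---|---|---|
| Table | Weeks 2–6 (days 14–42) | 42 − 14 = 28 | 14 − 14 = 0; at most 1, the night after Visit 2 |
| Visit 2 clause with stated Visit 3 date | Weeks 4–8 (days 28–56) | 42 − 28 = 14 (50%) | 28 − 14 = 14 |
| Table, but watch issued at Visit 1 (not stated) | Weeks 2–6 | 28 | 14 − 0 = 14 |

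On the second row the device is handed back 56 − 42 = 14 days before the course would end. The approximate sign on the visit intervals cannot absorb 14 days.

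**Watch wear.** Visit 1 to Visit 3 is 6 weeks, which just matches the battery. Visit 2 to Visit 4 is 8 weeks and Visit 1 to Visit 4 is 10 weeks; both exceed it.

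**Follow-up.** The table ends at Week 10, about 2.3 months. With treatment in Weeks 2 to 6 and a follow-up 3 months (about 13 weeks) after Visit 3, the study ends at Week 19, about 4.4 months. With the two-week delay and Visit 3 moved to Week 8, it ends at Week 21, about 4.8 months. Neither reaches 5 months, so the stated study length does not show which start date was meant.

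**Value of a baseline.** With baseline adjustment the standard error is multiplied by √(1 − r²), where r is the correlation between baseline and outcome. The protocol gives no r, so these values are assumed:

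- r = 0.3: 1 − √0.91 = 4.6% narrower interval
- r = 0.5: 1 − √0.75 = 13.4%
- r = 0.7: 1 − √0.51 = 28.6%

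**The case against.** The strongest reply is that this is stale numbering and not a broken design. The Visit 3 and Visit 4 text refers to measures taken at Visit 1. The consent bullet speaks of other Visit 1 activities, yet the table marks only consent there, with about 120 minutes allotted. If the whole block now headed Visit 2 was once Visit 1, the watch went out at Day 0 and use began at Week 2. That gives 14 baseline nights, all 28 sessions and a Week 6 outcome visit. It also suits the instruction to wear the watch throughout and the battery life of about 6 weeks.

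This is plausible and may well be what was intended. It is not what the document now says: the table has no watch mark at Visit 1, the actigraphy bullet sits under Visit 2, and the step-by-step guide has only consent at Visit 1. A reader might go to the other extreme and infer that the design cannot deliver both a baseline and a full course. The documents do not support that either, since moving the watch issue to Visit 1 delivers both.

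A second reply is that the half-course scenario is unlikely in practice. One clause stands against the table, the 28 hours, the Visit 3 date and the device return. Phone calls, diaries and the light loggers (lightbox arm only) would probably reveal a late start. That is fair, although none of those checks says which date is right.

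A statistical analysis plan, not available here, could define a baseline window. It could not supply nights or sessions that the visit schedule leaves out.

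**Conclusion.** The conflict stands as an internal inconsistency that should be fixed. Read literally, the Visit 2 clause leaves about 14 of 28 sessions before Visit 3. The table schedule leaves at most one untreated night of actigraphy. The date arithmetic needs no assumption beyond taking the visit intervals as stated.

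The consequences are limited. The randomised comparison with sham is valid on either schedule. On the table schedule the loss is confined to the actigraphy baseline, one part of Aim 1.

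A reader might infer that the missing baseline leaves the sleep-efficiency comparison underpowered. The protocol does not support a figure for that. At 50 per arm and two-sided 5%, illustrative power runs from 47% (effect size 0.38, no baseline) to above 99.9% (0.76, r = 0.7). The value 0.38 is the protocol's cited effect for sleep efficiency. The value 0.76 assumes that its quoted rise from 0.47 to 0.85 at 10,000 lux carries over: 0.38 + 0.85 − 0.47. What can be said is that a baseline would narrow the interval by about 5% to 29% if r lies between 0.3 and 0.7. Nor do the documents show that any participant was in fact treated on the wrong dates.

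**What to change.** Keep treatment in Weeks 2 to 6. Change the Visit 2 clause so that use starts the morning after Visit 2. Issue the watch and diary at Visit 1, and give the sleep-hygiene education then, so that the two baseline weeks follow it. Randomisation stays at Visit 2. Show this in the table and in the step-by-step guide.

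In the same edit:

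- Make the Visit 3 and Visit 4 text refer to measures taken at Visit 2.
- Choose one follow-up date, either 4 weeks after Visit 3 (Week 10) or 3 months after it (about Week 19), and bring the aims, the study length, the table and the Visit 4 text into line.
- State whether the watch is worn after Visit 3. The table issues one there, while the Visit 3 text and the step-by-step guide only collect it.

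**Cost.** Some watches go to consented people who are later excluded (up to 400 may be consented to reach 100), and watches must be mailed when Visit 1 is remote. Six weeks of wear reaches the battery life unless the watch is recharged or swapped at Visit 2. No visit, staff or participants are added, and Visit 1 already has time set aside.

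The alternative is to keep the two-week delay and move Visit 3 to Week 8. It also gives 14 baseline nights and 28 sessions, but is weaker. The baseline is recorded after randomisation with the device already at home, each schedule grows by two weeks, and the full battery is used with no visit in between.
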